8. ADVERSE EVENTS: LIST AND REPORTING REQUIREMENTS

An Adverse Event (AE) is any undesirable sign, symptom or medical condition or experience that develops or worsens in severity after starting the first dose of study treatment or any procedure specified in the protocol, even if the event is not considered to be related to the study.

Abnormal laboratory values or diagnostic test results constitute adverse events only if they induce clinical signs or symptoms or require treatment or further diagnostic tests.

Adverse events will be monitored from the time the subject signs informed consent. Subjects will be instructed to report all AEs during the study and subjects will be assessed for the occurrence of AEs throughout the study. All AEs (serious and non-serious) must be recorded on the source documents and case report forms regardless of the assumption of a causal relationship with the study drug.

Adverse Events that begin or worsen after informed consent should be recorded in the Adverse Events section of the case report form (CRF). Conditions that were already present at the time of informed consent should be recorded in the baseline symptoms section of the CRF. Adverse Event monitoring should be continued for at least 30 days following the last dose of study treatment. Adverse Events (including lab abnormalities that constitute AEs) should be described using a diagnosis whenever possible, rather than individual underlying signs and symptoms. When a clear diagnosis cannot be identified, each sign or symptom should be reported as a separate AE.

The following list of AEs (Section 8.1) and the characteristics of an observed AE (Section 8.2) will determine whether the event requires expedited reporting **in addition** to routine reporting.

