7.3 Ribociclib / Placebo

Management of severe or intolerable adverse reactions requires dose reduction, temporary interruption, and/or discontinuation of ribociclib therapy. Refer to the table below for guidance.

Dose modification guidelines: Dosing Levels

	Ribociclib/Placebo	
	Dose	Number of capsules/tablets & strength
Starting dose	600 mg	3 x 200 mg capsules/tablets
First dose reduction	400 mg	2 x 200 mg capsules/tablets
Second dose reduction	200 mg	1 x 200 mg capsules/tablets

Recommendations for dose reduction, interruption or discontinuation of ribociclib/placebo in the management of specific adverse reactions are summarized in the tables below. Definitions of grading of each Adverse Event are based on CTCAE 4.0. Clinical judgment of the treating physician should guide the management plan of each patient based on individual benefit/risk assessment.

If ribociclib is held, the cycle continues, as the patient will be taking hormone therapy. Missed doses of ribociclib will not be made up.

Subjects enrolled on Scenario 1a who are not able to tolerate ribociclib, despite dose reduction to the lowest dose (200 mg), will come off study and not be randomized to Scenario 1b.

Dose modification for hematologic adverse reactions:

LAB ABNORMALITY /	GRADE	DOSE ADJUSTMENT /
-------------------	-------	-------------------

TOXICITY		MANAGEMENT REC'S
Thrombocytopenia	Grade 1: ($\geq 75 \times 10^9/L$)	No dose adjustment required.
	Grade 2: ($\geq 50-75 \times 10^9/L$)	Dose interruption until recovery to grade ≤ 1 . Re-initiate ribociclib/placebo at the same dose.
	Grade 3: ($\geq 25-50 \times 10^9/L$)	Dose interruption until recovery to grade ≤ 1 . Re-initiate ribociclib/placebo at the same dose level. If grade 3 toxicity recurs, interrupt dose until recovery to grade ≤ 1 and then resume at next lower dose level.
	Grade 4: ($< 25 \times 10^9/L$)	Dose interruption until recovery to grade ≤ 1 . Re-initiate ribociclib/placebo at the next lower dose level. If toxicity recurs at grade 4: discontinue ribociclib/placebo.
Absolute Neutrophil Count*	Grade 1: ($\geq 1.5 \times 10^9/L$)	No dose adjustment required.
	Grade 2: ($\geq 1.0 - < 1.5 \times 10^9/L$)	No dose adjustment required.

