	Grade 3: ($\geq 0.5 - < 1.0 \times 10^9/L$)	Dose interruption until recovery to $\geq 1.0 \times 10^9/L$. Re-initiate ribociclib/placebo at the same dose level. If grade 3 toxicity recurs, interrupt dose until recover to $\geq 1.0 \times 10^9/L$. If resolved in ≤ 7 days, then resume at same dose level. If resolved in > 7 days, then resume at next lower dose level.
	Grade 4: ($< 0.5 \times 10^9/L$)	Dose interruption until recovery to $\geq 1.0 \times 10^9/L$. Re-initiate ribociclib/placebo at the next lower dose level. If toxicity recurs at grade 4: temporary dose interruption until recovery to $\geq 1.0 \times 10^9/L$ and reduce ribociclib/placebo to the next lower dose level.
Febrile Neutropenia*	Grade 3: ANC $< 1.0 \times 10^9/L$ with a single temperature of > 38.3 C or a sustained temperature of ≥ 38 C for more than one hour.	Dose interruption until improvement of ANC $\geq 1.0 \times 10^9/L$ and no fever. Restart at the next lower dose level. If febrile neutropenia recurs, discontinue ribociclib/placebo.
	Grade 4: Same as grade 3, with life threatening consequences.	Discontinue ribociclib/placebo.
Anemia**	Grade 1: Hgb ≥ 10.0 gm/dL	No dose adjustment required.

	Grade 2: Hgb \geq 8.0 - < 10.0 gm/dL	No dose adjustment required.
	Grade 3: Hgb <8 gm/dL	Dose interruption until recovery to grade \leq 2. Re-initiate ribociclib/placebo at the same dose.
	Grade 4: Life-threatening consequences	Discontinue ribociclib/placebo.

* Growth factor is allowed, per investigator discretion.

** Transfusion allowed, per investigator discretion.

Dose modification for hepatic toxicity:

Hepatic toxicity monitoring includes the following LFTs: albumin, ALT, AST, total bilirubin (fractionated if total bilirubin > 2 x ULN), alkaline phosphatase, and GGT. For patients with Gilbert Syndrome: total and direct bilirubin must be monitored with intensified monitoring applying to changes in direct bilirubin only.

** TOTAL BILIRUBIN without ALT/AST increase above baseline value. ULN=upper limit of normal.	
Grade 1 (> ULN – 1.5 x ULN) (confirmed 48-72h later)	Maintain dose level. Recheck LFTs every two weeks until resolved.

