For either continuous or intermittent dosing, the onset of neutropenia (most frequently Grade 2) occurs by Day 15, reaching a nadir in the third or fourth week with recovery during the week of drug holiday. Some patients require additional time for recovery (7 to 14 days). During this regime, growth factors are allowed.

QTc changes become evident in the first cycle by Day 8 and later (once steady state is reached), are associated with the maximum drug levels between 1 to 8 h post-dose, and remain stable or improve in subsequent cycles. Asymptomatic Grade 2 QTc prolongation was observed with increasing frequency at doses greater than 600 mg, and was considered the dose limiting toxicity. Two patients at 600 mg and two patients at 900 mg had asymptomatic QTc prolongation >500 ms (grade 3). One grade 1 atrioventricular block of first degree was reported as potentially related to ribociclib (at a dose of 140 mg). No other cardiac abnormalities were observed as related adverse events in any patient

There have been 4 deaths related to study drug reported as of April 2014. The following serious adverse events shown in the table below have been reported with a suspected causal relationship to ribociclib administration. For a complete list of AEs, all grades and Grade 3/4 that are suspected to be related to ribociclib refer to the Investigator Brochure.

Serious Adverse Events:

System Involved / Type of AE	Event(s)
Blood and lymphatic system	Anemia, febrile neutropenia, neutropenia, thrombocytopenia, Leukopenia, Lymphopenia
Gastrointestinal	Nausea, Vomiting, Diarrhea

Hepatobiliary disorders	Hepatic function abnormal Hepatocellular injury Cholecystitis
Investigations (incl. laboratory abnormalities)	Electrocardiogram QT prolonged Transaminases increased Blood creatinine increased

Severe, life-threatening, or fatal interstitial lung disease (ILD) and/or pneumonitis can occur in patients treated with KISQALI and other CDK4/6 inhibitors. Across clinical trials (MONALEESA-2, MONALEESA-3, MONALEESA-7), 1.1% of KISQALI-treated patients had ILD/pneumonitis of any grade, 0.3% had Grade 3 or 4, and 0.1% had a fatal outcome. Additional cases of ILD/pneumonitis have been observed in the postmarketing setting, with fatalities reported.

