8.2 Definitions and Reporting

8.2.1 Adverse Event (AE)

AEs will be assessed according to the Common Terminology Criteria for Adverse Events (CTCAE) version 4.0. The occurrence of AEs should be sought by non-directive questioning of the subject during the screening process after signing informed consent and at each visit during the study. As far as possible, each AE should be evaluated to determine:

- The severity grade (CTCAE Grade 1-5)
- Reasonable possibility that AE is related to the study treatment: Definite, Probable, Possible, Unlikely, Unrelated (Section 8.3.4)
- Start and end dates, unless unresolved at final exam

Action taken with respect to study drug (i.e., none, dose adjusted, temporarily interrupted, permanently discontinued, unknown, not applicable)

- Outcome (e.g., not recovered/not resolved, recovered/resolved, recovering/resolving, recovered/resolved with sequelae, fatal, unknown) the outcome ‘unknown’ should only be used when absolutely no data can be retrieved with regards to the event outcome e.g. if the subject is lost to follow-up.
- Whether it is serious, as per Serious Adverse Event (SAE) definition provided below.

Unlike routine safety assessments, SAEs are monitored continuously and have special reporting requirements, see Section 8.2.2.

All AEs should be treated appropriately. If a concomitant medication or non-drug therapy is given, this action should be recorded on the AE CRF as well as the Prior/Concomitant medications CRF.

Once an AE is detected, it should be followed until its resolution or until it is judged to be permanent; assessment should be made at each visit (or more frequently if necessary) of any changes in severity, the suspected relationship to the study drug, the interventions required to treat it, and the outcome.

Disease progression should not be regarded or reported as an AE itself, unless it is associated with a separate AE.

Laboratory abnormalities that constitute an AE in its own right (are considered clinically meaningful, induce clinical signs or symptoms, require concomitant therapy or require changes in study treatment), should be recorded on the AE CRF. Whenever possible, a diagnosis, rather than a symptom should be provided (i.e., anemia instead of low hemoglobin). Laboratory abnormalities that meet the criteria for AEs should be followed until they have returned to normal or an adequate explanation of the abnormality is found.

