When an abnormal laboratory or test result corresponds to a sign or symptom of a previously reported AE, it is not necessary to separately record the lab/test result as an additional event.

Laboratory abnormalities that do not meet the definition of an AE should not be reported as AEs. A Grade 3 or 4 (severe) event, as per CTCAE, does not automatically indicate a SAE unless it meets the definition of serious, as defined below, and/or as per the investigator's discretion.

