13.3 Evaluation of Toxicity

The frequency of subjects experiencing toxicities will be tabulated.

The case report form will be utilized for AE reporting, based upon the CTEP Active Version of the NCI Common Terminology Criteria for Adverse Events (CTCAE) v4.0.

The descriptions and grading scales in CTEP Version 4.0 of the CTCAE can be located on the CTEP website at: http://ctep.cancer.gov/protocolDevelopment/electronic_applications/ctc.htm.

All patients will be evaluable for toxicity from the time of their first treatment with the investigational drug.

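### Sections 8 and 8.2.1 set different criteria for a laboratory adverse event, so asymptomatic blood-count toxicity managed only by a dose hold may be recorded at one site and not at another

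*Combined protocol and SAP*

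**What the plan says.** The opening of Section 8 is exclusive: abnormal laboratory or test results "constitute adverse events only if they induce clinical signs or symptoms or require treatment or further diagnostic tests".

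Section 8.2.1 tells sites to record laboratory abnormalities that "are considered clinically meaningful, induce clinical signs or symptoms, require concomitant therapy or require changes in study treatment". It then adds: "Laboratory abnormalities that do not meet the definition of an AE should not be reported as AEs".

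Section 13.3 plans the analysis in one line, "The frequency of subjects experiencing toxicities will be tabulated", and names the case report form as the vehicle for adverse event reporting. No analysis of graded laboratory values is planned. Objective 4 in Section 1.2.2 concerns adverse event rates and tolerability with and without ribociclib, and Section 13.1 calls the adverse event rate exploratory.

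For neutropenia, the Section 7.3 table gives "No dose adjustment required" at grades 1 and 2. It calls for a dose interruption at grade 3, and for an interruption followed by a lower dose level at grade 4. A footnote says "Growth factor is allowed, per investigator discretion". Section 8.1 says of ribociclib that "the onset of neutropenia (most frequently Grade 2) occurs by Day 15", with recovery usually in the drug-free week.

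**The concern.** Both definitions are current text, neither refers to the other, and nothing says which governs. The bar on reporting in 8.2.1 turns a difference in wording into a difference in data, because an abnormality that fails whichever definition a site applies is not entered at all.

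The trial is blinded, so a site cannot apply one rule to one arm and another rule to the other. The imbalance would come from frequency: asymptomatic low counts are expected mostly on ribociclib, so events dropped under the Section 8 rule would come mostly from that arm. The between-arm excess in Section 13.3 would then be understated, to a degree that depends on how each of the 11 centers reads the protocol.

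**Working it through.** The plan gives no figure to reproduce. The check sets the two definitions side by side and applies them to the courses that Section 7.3 and the study calendar would produce.

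**Criteria**
- In both: signs or symptoms; need for treatment or concomitant therapy.
- Only in Section 8: need for further testing.
- Only in 8.2.1: judged clinically meaningful; change in study treatment.

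Neither list is a subset of the other.

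**Applied to asymptomatic courses**

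| Course | Section 8 | Section 8.2.1 |
|---|---|---|
| Grade 1–2 neutropenia, scheduled counts only | No | Only if judged clinically meaningful |
| Grade 3 neutropenia, hold only, recovery seen at a scheduled count | No | Yes (treatment changed) |
| Grade 3 neutropenia, hold plus an unscheduled repeat count | Arguably yes (further test) | Yes |
| Grade 3 neutropenia, hold plus growth factor | Yes (treatment) | Yes |
| Grade 4 neutropenia | Depends, as for grade 3 | Yes |
| Grade 1 bilirubin, dose kept, rechecks every two weeks | Arguably yes (further tests) | Only if judged clinically meaningful |

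The second row is the clear conflict. It assumes that a hold is not itself treatment in the Section 8 sense. Grade 2–3 thrombocytopenia, and grade 3 anemia held without transfusion, fall in the same row. For grade 4, Section 8.2.8 asks for reporting to the coordinating center as for serious events unless the event is expected and specifically exempted, so those cases should surface under either definition.

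**Is the second row a realistic course?** Section 10 schedules counts at Cycle 1 Day 15 and Cycle 2 Day 1. With 28-day cycles, Cycle 2 Day 1 is day 29, and 29 − 15 = 14 days later. Those 14 days hold the remaining dosing days 15–21 (7 days) and the drug-free days 22–28 (7 days). A first grade 3 episode at Day 15 can therefore be held, recover in the off week and be confirmed at the next scheduled count, with no growth factor and no extra test.

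The course is less likely elsewhere. For a repeat episode ("If grade 3 toxicity recurs, interrupt dose until recover to" the stated threshold), the restart level depends on whether recovery took more than 7 days. Counts 14 days apart cannot show that, so an unscheduled count is needed and Section 8 is arguably met. From Cycle 3 the scheduled counts are 28 days apart, which again favors an extra test. The conflict is therefore concentrated in first episodes at the Day 15 counts: Cycle 1 in both scenarios, and also Cycle 2 in the Scenario 2 calendar.

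**Size.** With 120 randomized 1:1 there are 60 patients on ribociclib. Section 8.1 gives 47.7% neutropenia of any grade on ribociclib monotherapy, and 60 × 0.477 ≈ 29 patients. Section 5.5 reports grade 2/3 neutropenia in 6 of 7 patients (85.7%) on ribociclib plus fulvestrant. These figures illustrate the pool from which second-row cases would come. They are not the number lost. The share that is asymptomatic, handled by a hold alone and rechecked only on schedule is not given anywhere, so the shortfall can lie anywhere from zero up to the number of such cases.

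**The case against.** The best defense is that the surrounding text leans toward 8.2.1. The reporting bar sits inside 8.2.1, so the definition it mentions is most naturally the one given there. The same section lists temporary interruption among the actions recorded for an adverse event, and Section 7.3 files these events under hematologic adverse reactions. Many sites will therefore record a held dose as an adverse event. In addition, dose changes go on their own form (Section 7), Section 12.2 refers to laboratory data entered on case report forms, and after the August 2023 unblinding sites enter only serious events and status updates (Section 6.6). Changing the definition now would alter few non-serious records.

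This limits the likely size, and it means that rewording alone would achieve little. It does not remove an exclusive rule in Section 8 that nothing overrides. It also shows that the remedy should rest on counts already collected.

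Some stronger readings are tempting but unsupported:
- From Section 2.3, a reader might pair neutropenia of 78% versus 4% with febrile neutropenia of 0.6% and infer that the recorded rate could fall anywhere from a few percent to about 80%. Section 8 is not a fever-only rule, because it also counts treatment and further tests. The figures come from a palbociclib trial whose recording rule is not given. Section 8.2.1 does not capture every grade 1–2 case either.
- A reader might call neutropenia the main ribociclib toxicity. Section 8.1 ranks it third, after fatigue (53.8%) and nausea (50.8%), and names QTc prolongation as dose limiting. It is fairly called a leading toxicity.
- A reader might extend the shortfall to hepatic and QTc events. Section 7.3 mostly requires extra tests for these, so Section 8 would usually capture them.
- A reader might take 8.2.1 as simply the wider definition. It lacks the further-tests criterion.

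**Conclusion.** The contradiction is real, is in current text, and changes how a plausible hematological course is classified. Asymptomatic blood-count toxicity managed only by a hold, with recovery seen at a scheduled count, is reportable under 8.2.1 and excluded under Section 8. The Section 13.3 comparison can therefore vary by site and understate the excess on ribociclib.

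The size cannot be computed from the documents. It is zero if every site follows 8.2.1 or orders an unscheduled count after each hold. Otherwise it grows with the number of hold-only cases at sites following Section 8. The direction rests on one assumption, that asymptomatic low counts are much more common on ribociclib than on placebo. Grade 4 events are largely protected by the Section 8.2.8 route. The primary PFS analysis, its alpha and its power are not touched. The effect is on an exploratory safety endpoint, but one that supports the tolerability objective, and the correction is cheap.

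**What to change.** 1. Reconcile Section 8 and Section 8.2.1 into one laboratory adverse event definition, stated once and cross-referenced, so that the bar on reporting in 8.2.1 points to a single rule.
2. In Section 13.3, add a by-arm table of worst post-randomization CTCAE grade for neutrophils, platelets and hemoglobin, derived from the protocol blood counts and independent of what was entered on adverse event forms. For patients on treatment at the August 2023 unblinding, use counts up to that point, because the protocol schedule and routine data entry stop there. Section 7.3 describes grade 4 anemia by its clinical consequences, so the hemoglobin rows can be derived from counts only up to grade 3.
3. Similar hepatic and QTc tables are optional, since under-recording of those is not shown.

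The cost is a wording change and one derived table. The blood counts are already scheduled in Section 10, so no new assessment is needed. This assumes that the count values are held in the trial database, as Section 12.2 indicates. The second item does most of the work, because it does not depend on which definition a site followed and it also covers data already collected.

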8.1 Synopsis of Common Adverse Events with the study drugs

Synopsis of common adverse events with ribociclib:

Below is a synopsis of common adverse events in patients being treated with ribociclib, as provided in the investigator's brochure (IB).

Ribociclib is currently being investigated in patients as a single agent in 3 phase I studies, and in combination in 10 studies, including 8 phase Ib/II studies, a randomized phase II study, and a randomized phase III study (MONALEESA-2). Ribociclib is also being investigated in 3 clinical pharmacology studies in healthy subjects. Details on these studies can be found in the ribociclib IB, Section 5.1 and Section 5.2.

In single agent trials, a total of 196 patients have been treated. Ribociclib is also being evaluated in several combination trials with: letrozole, with letrozole and the PI3K inhibitor BYL719, with letrozole and the PI3K inhibitor buparlisib, with fulvestrant and buparlisib, with the mTOR inhibitor everolimus and exemestane, with LGX818, with MEK162, and with MEK162 and LGX818. The results of the phase I combination of letrozole and ribociclib are detailed in the IB.

In the phase I monotherapy trials, patients with metastatic solid tumors or lymphomas were treated with increasing doses of ribociclib orally, once daily for 21 days followed by a 7-day off-drug period (28-day cycles). Doses ranging from 50 mg to 1200 mg were evaluated. In addition, continuous dosing of ribociclib at 600 mg was evaluated. Treatment has been discontinued in 111 of 132 patients (84%); the primary reasons for treatment discontinuation were: progression of disease (72%), adverse events (6%); withdrawal of consent (2%); and loss to follow up (1%).

The most frequently reported AEs ($\geq 10\%$), regardless of grade, causality and ribociclib dose were:

- Fatigue (53.8%)
- Nausea (50.8%)
- Neutropenia (47.7%)
- Leukopenia (46.2%)
- Anemia (37.1%)
- Vomiting (34.8%)
- Thrombocytopenia (34.1%)
- Diarrhea (32.6%)
- Lymphopenia (30.3%)
- Decreased appetite (21.2%)
- Hyperglycemia (21.2%)
- Constipation (19.7%)
- Hypoalbuminemia (18.9%)
- Dyspnea (18.2%)
- Cough (16.7%)
- Fever (15.9%)
- Rise in serum creatinine (15.9%)
- Abdominal pain (15.2%)
- aspartate aminotransferase increase (15.2%)
- Edema (15.2%)
- Headache (15.2%)
- Back pain (14.4%)
- Dizziness (13.6%)
- QTc prolongation (11.4%)
- Alkaline phosphatase increase (10.6%)
- Hypocalcemia (10.6%)

For either continuous or intermittent dosing, the onset of neutropenia (most frequently Grade 2) occurs by Day 15, reaching a nadir in the third or fourth week with recovery during the week of drug holiday. Some patients require additional time for recovery (7 to 14 days). During this regime, growth factors are allowed.

QTc changes become evident in the first cycle by Day 8 and later (once steady state is reached), are associated with the maximum drug levels between 1 to 8 h post-dose, and remain stable or improve in subsequent cycles. Asymptomatic Grade 2 QTc prolongation was observed with increasing frequency at doses greater than 600 mg, and was considered the dose limiting toxicity. Two patients at 600 mg and two patients at 900 mg had asymptomatic QTc prolongation >500 ms (grade 3). One grade 1 atrioventricular block of first degree was reported as potentially related to ribociclib (at a dose of 140 mg). No other cardiac abnormalities were observed as related adverse events in any patient

There have been 4 deaths related to study drug reported as of April 2014. The following serious adverse events shown in the table below have been reported with a suspected causal relationship to ribociclib administration. For a complete list of AEs, all grades and Grade 3/4 that are suspected to be related to ribociclib refer to the Investigator Brochure.

Serious Adverse Events:

System Involved / Type of AE	Event(s)
Blood and lymphatic system	Anemia, febrile neutropenia, neutropenia, thrombocytopenia, Leukopenia, Lymphopenia
Gastrointestinal	Nausea, Vomiting, Diarrhea

Hepatobiliary disorders	Hepatic function abnormal Hepatocellular injury Cholecystitis
Investigations (incl. laboratory abnormalities)	Electrocardiogram QT prolonged Transaminases increased Blood creatinine increased

Severe, life-threatening, or fatal interstitial lung disease (ILD) and/or pneumonitis can occur in patients treated with KISQALI and other CDK4/6 inhibitors. Across clinical trials (MONALEESA-2, MONALEESA-3, MONALEESA-7), 1.1% of KISQALI-treated patients had ILD/pneumonitis of any grade, 0.3% had Grade 3 or 4, and 0.1% had a fatal outcome. Additional cases of ILD/pneumonitis have been observed in the postmarketing setting, with fatalities reported.

Reported frequency includes the cases reported with the following terms: pneumonitis, interstitial lung disease, pulmonary fibrosis, organizing pneumonia, acute respiratory distress syndrome (ARDS), interstitial pneumonia, pleural fibrosis. Novartis frequency includes only those events which occurred according to the broad SMQ for ILD/pneumonitis and included the following terms: ARDS, alveolitis, hypersensitivity pneumonitis, interstitial lung disease, lung infiltration, pneumonitis, pulmonary fibrosis.

Additionally, the 1 death reported in MONALEESA-3 (originally published in J Clin Oncol on August 20, 2018) was classified as acute respiratory distress syndrome in a patient who had lung metastases.

Synopsis of common adverse events with fulvestrant:

Fulvestrant is very well tolerated. Below is a table of common adverse events in patients being treated with fulvestrant 250 mg (N=374) and 500 mg (N=362), as reported in the phase III CONFIRM trial.⁷⁵ The only grade 3 toxicities that occurred in greater than 1% of patients were joint disorders/pain and GI disturbances.

Adverse Event	Fulvestrant 500 mg (n = 361)				Fulvestrant 250 mg (n = 374)			
	Grade 1-4		≥ Grade 3		Grade 1-4		≥ Grade 3	
	No. of Patients	%	No. of Patients	%	No. of Patients	%	No. of Patients	%
Endometrial dysplasia	0	0	0	0	0	0	0	0
GI disturbances	73	20.2	8	2.2	76	20.3	1	0.3
Hot flashes	30	8.3	0	0	23	6.1	0	0
Injection site reactions	49	13.6	1	0.3	50	13.4	0	0
Ischemic cardiovascular disorders	5	1.4	0	0	7	1.9	3	0.8
Joint disorders	68	18.8	8	2.2	70	18.7	8	2.1
Osteoporosis	1	0.3	0	0	0	0	0	0
Thromboembolic events	3	0.8	2	0.6	6	1.6	4	1.1
Urinary tract infection	8	2.2	1	0.3	8	2.1	1	0.3
Vaginitis	3	0.8	0	0	1	0.3	0	0
Weight gain	1	0.3	0	0	1	0.3	0	0

Synopsis of common adverse events with letrozole and exemestane:

Common adverse events are similar amongst all 3 aromatase inhibitors (anastrozole, letrozole, and exemestane)

Below is a synopsis of common adverse events reported in patients being treated with letrozole and exemestane, based on extensive post-marketing experience, according to the Prescribing Information. While serious adverse event rates are considerable, the vast majority of serious AEs are not clearly treatment related. Moreover, as patients are frequently treated with letrozole for 5 to 10 years in the adjuvant setting, the cumulative incidence of non-treatment related adverse events can be considerable. Adverse events reported in clinical trials with shorter durations of follow up are quite comparable to those seen with other AIs and with fulvestrant.

Adverse Events Reported in >10% of patients:

Cardiovascular: Edema (7% to 18%)

Central nervous system: Headache (4% to 20%), dizziness (3% to 14%), fatigue (8% to 13%)

Endocrine & metabolic: Hypercholesterolemia (3% to 52%), hot flashes (6% to 50%)

Gastrointestinal: Nausea (9% to 17%), weight gain (2% to 13%), constipation (2% to 11%)

Neuromuscular & skeletal: Weakness (4% to 34%), arthralgia (8% to 25%), arthritis (7% to 25%), bone pain (5% to 22%), back pain (5% to 18%), bone mineral density decreased/osteoporosis (5% to 15%), bone fracture (10% to 14%)

Respiratory: Dyspnea (6% to 18%), cough (6% to 13%)

Miscellaneous: Diaphoresis (\leq 24%), night sweats (15%)

Adverse Events Reported in 1 to 10% of patients:

Cardiovascular: Chest pain (6% to 8%), hypertension (5% to 8%), chest wall pain (6%), peripheral edema (5%); cerebrovascular accident including hemorrhagic stroke, thrombotic stroke (2% to 3%);

thromboembolic event including venous thrombosis, thrombophlebitis, portal vein thrombosis, pulmonary embolism (2% to 3%); MI (1% to 2%), angina (1% to 2%), transient ischemic attack

Central nervous system: Insomnia (6% to 7%), pain (5%), anxiety ($<$ 5%), depression ($<$ 5%), vertigo ($<$ 5%), somnolence (3%)

Dermatologic: Rash (5%), alopecia (3% to 5%), pruritus (1%)

Endocrine & metabolic: Breast pain (2% to 7%), hypercalcemia ($<$ 5%)

Gastrointestinal: Diarrhea (5% to 8%), vomiting (3% to 7%), weight loss (6% to 7%), abdominal pain (6%), anorexia (1% to 5%), dyspepsia (3%)

Genitourinary: Urinary tract infection (6%), vaginal bleeding (5%), vaginal dryness (5%), vaginal hemorrhage (5%), vaginal irritation (5%)

Neuromuscular & skeletal: Limb pain (4% to 10%), myalgia (7% to 9%)

Ocular: Cataract (2%)

Renal: Renal disorder (5%)

Respiratory: Pleural effusion ($<$ 5%)

Miscellaneous: Infection (7%), influenza (6%), viral infection (6%), secondary malignancy (2% to 4%)

Adverse Events Reported in < 1% of patients:

Anaphylactic reaction, angioedema, arterial thrombosis, cardiac failure, carpal tunnel syndrome, endometrial cancer, endometrial hyperplasia, endometrial proliferation, erythema multiforme, hepatitis, leukopenia, memory impairment, stomatitis, tachycardia, thrombocytopenia, toxic epidermal necrolysis, trigger finger

Adverse events reported in the phase III study of letrozole vs. tamoxifen in the first line setting for metastatic breast cancer in post-menopausal patients with a median follow up of 32 months is reported below.⁸²

Table 4. Adverse Events Including Bone-Related Occurrences

Adverse Event	Letrozole (n = 455)		Tamoxifen (n = 455)	
	No. of Patients	%	No. of Patients	%
Irrespective of relationship, reported by ≥ 10% patients				
Bone pain	99	22	95	21
Hot flushes NOS	84	19	74	16
Back pain	82	18	86	19
Dyspnea	81	18	79	17
Nausea	78	17	77	17
Arthralgia	71	16	67	15
Cough	61	13	59	13
Fatigue	58	13	59	13
Constipation	45	10	48	11
Suspected to be related, reported by ≥ 5% patients				
Hot flushes	76	17	65	14
Nausea	30	7	29	6
Patients reporting bone fractures, any relationship				
Patient-years of treatment	562.3		420.9	
Fracture rate per patient-year (95% CI)	0.0427 (0.0241 to 0.0613)		0.0451 (0.0260 to 0.0640)	

Abbreviations: NOS, not otherwise specified; CI, confidence interval.

